## 9. Correlative Studies

*Correlative studies obtained will depend on available of Personal protective equipment (PPE) available for research staff and laboratory supplies available for research. Testing will be done according to the study calendar (section 10).*

- 1) Naso/pharyngeal swabs and sputum/blood will be collected, pending available resources. Both investigational drugs are anticipated to disrupt viral replication, leading to a decrease in viral load with a faster time to a negative test/viral clearance. To assess this we will look at viral kinetics with sampling per study calendar (section 10) (nasopharyngeal, sputum, blood).
  - a. Viral load (quantitative)
  - b. Viral clearance
- 2) Peripheral Blood (~10cc): Serum and viably frozen PBMC fractions will be prepared from blood draws. We will evaluate:
  - a. Serum hormone determination of estradiol, testosterone (free and total), luteinizing hormone and follicle stimulating hormone. We hypothesize that bicalutamide administration will elevate estrogen levels within days of therapy initiation, which can engage pro-repair function in Tregs and other immune cell populations. Although there is robust data on estrogen elevation in patients treated with bicalutamide for prostate cancer, there is no data examining this in an acute timeframe.
  - b. Serum antibody titers (and follow-up periods, if available)
  - c. Serum measurement of cytokines (Mesoscale MSD)
  - d. When sufficient sample available, MANAFEST assay for viral reactive T cell receptors and immunophenotyping
  - e. When sufficient sample available, single cell RNA-seq of PBMC
  - f. Additional aliquots of serum and PBMCs will be banked

## 10. Study Calendar

	Day of study										
	Baseline/ screening	Treatment							Follow up ( $\pm$ 3 days)		
		-3 to 0	1	2	3	4	5	6	7 &	21	60
Eligibility	X										
Consent	X										
Randomization and drug dispensing*	X										
COVID-19 symptoms	X ^				X				X	X	X
Follow-up visit (can be in person, via telephone or via telemedicine)**				X					X	X	X
Review of medical record for hospitalization, death, etc a								X			
Both arms standard of care		X	X	X	X	X	X	X			
Experimental arm: Bicalutamide + camostat Treatment		X	X	X	X	X	X	X			
Adverse events, con meds (including OTC medications), new infections***			X						X	X	X
COVID-19 nasopharyngeal swab ^^	X								X	X	
Clinical and study blood collection (CMP b , CBC and differential, coagulation, d-dimer, CK, CRP, ESR, ferritin) ^^		X							X	X	
Ultrasensitive PSA + sex hormones c^^	X								X	X	
COVID-19 RNA testing (quantitative and qualitative) from blood, oral samples for research) ^^	X								X	X	
Additional research blood draw (1 tube) ^^	X								X	X	
SARS-CoV-2 antibody analysis ^^	X								X	X	

\*Study drug may be shipped to the patient. See section 4.6 for information relevant to drug dispensing.

Review of remaining pills and Study Drug Patient Diary may be conducted during a telemedicine visit.

Copies of the Study Drug Patient Diary may be submitted to study staff by phone, email, fax, or mychart

\*\*If patients are admitted, we will get information from the medical record.

\*\*\*Any new infection that occurs on study will be recorded. The site of infection and the source of culture (ie BAL, tracheal aspirate, sputum, blood, urine, etc.) will be recorded as well.

aThe following will be recorded daily (as available) from hospital records: symptoms (see Appendix A), temperature, heart rate, respiratory rate, systolic blood pressure, diastolic blood pressure, oxygen saturation, height, weight, oxygen requirements and supplementary oxygen use, procedures (including intubation, renal replacement therapy, vasopressor/inotropic support, ECMO, etc), intermediate care unit duration, intensive care unit duration

bCMP: Na, K, Cl, BUN, Cr, Ca, Tot Protein, Alb, bilirubin, AST, ALT, Alk phos, CO2

cSex hormones: estradiol, free testosterone, total testosterone, FSH, LH

& Day 7 labs may be collected +/- 3 days

^ Record the number of days between the onset of symptoms and initiation of treatment.

^^Optional: depending on availability of supplies and facilities (PPE and laboratory equipment availability for research). If obtained for clinical reasons, will record results.

In order to minimize the need for research-only in-person visits, telemedicine visits may be substituted for in person clinical trial visits or portions of clinical trial visits where determined to be appropriate and where

determined by the investigator not to increase the participants risks. Prior to initiating telemedicine for study visits the study team will explain to the participant, what a telemedicine visit entails and confirm that the study participant is in agreement and able to proceed with this method. Telemedicine acknowledgement will be obtained in accordance with the Guidance for Use of Telemedicine in Research. In the event telemedicine is not deemed feasible, the study visit will proceed as an in-person visit. Telemedicine visits will be conducted using HIPAA compliant method approved by the Health System and within licensing restrictions.

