## 2.6. Exploratory endpoints

Attenuation in disease course/inflammatory response –*resources permitting*

- Change from baseline in white blood cells, platelets, D-dimer, AST, ALT, CK, CRP, ESR, ferritin
- Change from baseline in hormones and hormone regulated gene expression
- Immunophenotyping of PBMCs with fluorescence-activated cell sorting (FACS): to understand the immune response and to determine the source of critical cytokines (resources permitting)
- SARS-CoV-2 antibody analysis, including IgM to IgG transition and virus-neutralizing antibodies

Clinical exploratory endpoints

- Duration of hospitalization (defined as number of calendar days in the hospital)
- % of patients needing upgrade to the intermediate care unit (IMC)
- Duration of IMC stay
- % of patients needing upgrade to the intensive care unit (ICU)
- Duration of ICU stay
- % of patients with need for mechanical ventilation
- Duration of mechanical ventilation

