#### 6.6. End of initial treatment

After 7 days of oral therapy, treatment will stop and patients will be followed as per section 10 (study calendar).

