### 11.2. Analysis of the secondary and exploratory endpoints

The proportion of people with symptoms will be compared to the proportion of people without symptoms and compared using chi-squared test. Proportions with drug-related adverse events and serious adverse events will be compared using chi-squared test. All-cause mortality at day 60 will be compared using Fisher's exact test and a time to event analysis using Kaplan-Meier methods will be used to compare the two arms.

Descriptive statistics will be used to summarize and compare the exploratory endpoints.

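### Exploratory laboratory and hormone endpoints use change from baseline where baseline adjustment would be more precise, and day-7 samples mix on-treatment and post-treatment draws

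*Combined protocol and SAP*

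**What the plan says.** Section 2.6 lists two relevant groups of exploratory endpoints: "Change from baseline in white blood cells, platelets, D-dimer, AST, ALT, CK, CRP, ESR, ferritin" and "Change from baseline in hormones and hormone regulated gene expression". Section 11.2 gives their whole analysis: "Descriptive statistics will be used to summarize and compare the exploratory endpoints". It names no baseline covariate and makes no use of the actual sampling day.

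The study calendar in section 10 places the follow-up samples at day 7 and day 21. Its footnote to the day-7 column reads "Day 7 labs may be collected +/- 3 days". Section 6.6 states: "After 7 days of oral therapy, treatment will stop". A nominal day-7 sample drawn on days 4 to 7 is therefore on treatment, and one drawn on days 8 to 10 is after it.

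The samples are not guaranteed. The calendar marks them "Optional: depending on availability of supplies and facilities", and section 2.6 makes the laboratory and immune endpoints conditional on resources.

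**The concern.** There are two separate issues.

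**Precision.** A change score subtracts the whole baseline value, which is right only if the regression slope of follow-up on baseline is 1. When the correlation is moderate, as it can be for markers that move during an acute infection, subtraction adds baseline noise. With at most 20 patients per arm, and fewer if optional samples are missed, that loss is worth avoiding, and the baseline values it needs are the same ones the change score uses.

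**Interpretation.** Section 9 hypothesises that estrogen rises within days of starting bicalutamide and notes the lack of data over an acute period. A day-7 summary that pools mid-treatment samples with samples up to three days after the last dose blurs the readout meant to test this.

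What is at stake is the quality of mechanistic estimates. Section 11 says the trial's estimates will inform a larger one. No test, sample size or decision in the plan rests on these readouts.

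**Working it through.** **Plan's own figure.** The documents state no precision or power for these endpoints. The only power figure, 80% in section 11, concerns hospitalization; exact enumeration of the one-sided Fisher test (20 per arm, 20% against 2%, alpha 0.25) gives 80.3%. It has no bearing on this point.

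**Inputs from the documents.** 40 patients (section 3), allocated 1:1 (6.2), so 20 per arm. Window of 7 ± 3 days (10). Treatment for 7 days (6.6). Half-life of active R-bicalutamide 5.9 days with normal hepatic function (8.2). Half-life of camostat's active metabolite about 100 minutes (8.1).

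**Assumptions.** Equal standard deviation σ at baseline and follow-up, and correlation ρ between them, varied from 0.3 to 0.9.

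**1. Change score against ANCOVA**

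- Variance of a change score: 2(1 − ρ)σ².
- Residual variance after adjusting for baseline: (1 − ρ²)σ².
- Ratio: (1 − ρ²) / [2(1 − ρ)] = (1 + ρ)/2.

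| ρ | Change (σ²) | ANCOVA (σ²) | Ratio | Variance cut | Power, change | Power, ANCOVA |
|---|---|---|---|---|---|---|
| 0.3 | 1.40 | 0.91 | 0.65 | 35% | 57% | 76% |
| 0.5 | 1.00 | 0.75 | 0.75 | 25% | 72% | 83% |
| 0.7 | 0.60 | 0.51 | 0.85 | 15% | 90% | 94% |
| 0.9 | 0.20 | 0.19 | 0.95 | 5% | near 100% | near 100% |

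The power columns only illustrate scale: 20 per arm, assumed effect 0.8σ, two-sided 0.05, normal approximation. At ρ = 0.5, the standard error for change is σ√(2/20) = 0.316σ, and 0.8/0.316 − 1.96 = 0.57, giving 72%. For ANCOVA it is 0.316 × √0.75 = 0.274σ, and 0.8/0.274 − 1.96 = 0.96, giving 83%.

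These ratios ignore the cost of estimating the slope. In simulation with 8 per arm and ρ = 0.8, the standard errors were 0.315 (change) and 0.313 (ANCOVA), so the gain almost disappears when both evaluable numbers are small and correlation is high.

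**2. What the window mixes**

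For one daily dose and a one-compartment model, the bicalutamide level as a fraction of steady state on day d ≤ 7 is 1 − 2^(−d/5.9). Day 4 gives 37.5% and day 7 gives 56.1%. After the last dose it decays: day 10 is 56.1% × 2^(−3/5.9) = 39.4%. Relative to day 7:

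| Day | 4 | 5 | 6 | 7 | 8 | 9 | 10 |
|---|---|---|---|---|---|---|---|
| Level | 67% | 79% | 90% | 100% | 89% | 79% | 70% |

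The mean over the seven days is 82%. Camostat's metabolite passes 24 × 60/100 = 14.4 half-lives in 24 hours, so it is effectively absent in post-treatment samples.

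**3. Does a sampling-day covariate repair this?**

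- *Trend common to both arms.* Uniform sampling over days 4 to 10 has a standard deviation of 2.0 days. An assumed slope of 0.1, 0.2 or 0.3 SD per day adds (slope × 2)² = 0.04, 0.16 or 0.36 σ², which is 4%, 16% or 36% of the change-score variance at ρ = 0.5. A linear day term recovers most of it: at 0.2 SD per day, 20 per arm and ρ = 0.5, the simulated ANCOVA standard error falls from 0.306 to 0.282. If there is no trend, the term costs about 1–2% in standard error at 20 per arm and 3–4% at 8.
- *On/off-drug part.* The levels above rise and then fall. The least-squares slope is about 0.3 percentage points per day and explains about 0.3% of their variance. If a treatment effect tracks drug level (an assumption), the estimate averages 0.82 of its day-7 value, and simulation shows it still at 0.82 with a linear day term. An arm-by-off-drug term moves it only to 0.86 and raises the standard error from 0.279 to 0.366 (20 per arm, ρ = 0.5).

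**The case against.** The strongest reply is that these endpoints are optional, exploratory and openly descriptive in a 40-patient study. Nothing is tested on them, and section 11.2 does not prevent reporting by sampling day. The correlations are assumed, neither drug's concentration is measured, and the documents give no link from drug level to hormones or inflammatory markers. Optional baselines shrink an adjusted analysis further. All of this stands, and it makes the point a minor one. It does not make the change score the better choice where the correlation is moderate, because a change score needs the same baseline sample.

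A reader might infer more than the documents support:

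- *That timing noise can be adjusted away at no cost.* Only a trend common to both arms can be removed cheaply. The on/off-drug part exists only in the treated arm, is not linear in day, and is expensive to model at this size.
- *That the arms are sampled at different times.* Both follow the same calendar. Return of study drug does not imply an extra visit, since section 4.6 allows pill review by telemedicine. Section 6.2 lets treatment start up to 72 hours after randomization, so days since randomization need not equal days on drug. That is a reason to record both, not evidence of imbalance.
- *That the plan specifies a time-to-negative or change-from-baseline viral analysis.* Section 9 offers "faster time to a negative test/viral clearance" as an anticipated effect. The readouts it lists are quantitative viral load and viral clearance, with no change-from-baseline scale, and section 2.6 does not list them. The window footnote speaks of labs, so its application to swabs is not explicit.

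**Conclusion.** The point holds as a low-cost improvement to exploratory analyses. Replacing change scores with baseline-adjusted values cuts variance by (1 − ρ)/2: 35% at ρ = 0.3, down to 5% at ρ = 0.9. This assumes equal variances, a correlation the documents do not give, and enough evaluable patients for the slope to be estimated at little cost.

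The day 4 to 10 window does mix on-treatment and post-treatment samples. How far this dilutes a hormone or laboratory effect is unknown; the 0.82 figure applies only if the effect tracks bicalutamide level and draws are spread evenly over the window. The remedy for that part is recording and transparent display, not a covariate. The primary endpoint and sample size are unaffected.

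**What to change.** In section 11.2:

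1. Compare day-7 and day-21 laboratory and hormone values between arms by ANCOVA with the baseline value as covariate, on a suitable scale (for example, logarithms for skewed markers). Report the adjusted difference or ratio with a confidence interval, labelled exploratory.
2. Show treated-arm day-7 samples drawn on treatment and after the last dose separately.
3. Use actual sampling day as a covariate in a sensitivity analysis only, and state that it addresses a time trend shared by both arms and not the on/off-drug dilution.

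In section 10 or the case report form, record the actual sampling day relative to randomization and, in the treated arm, to first and last dose.

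The sampling window, visits and number of samples stay as they are. The cost is analysis wording and a few recorded dates. The downside is that patients without the optional baseline sample are left out of the adjusted comparison and are shown descriptively; the number per arm should be reported. If few patients have paired samples, the gain may be negligible.

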### 1.1. Camostat

[figure not shown]
Camostat mesilate is a serine protease inhibitor. It is approved for use in Japan for the treatment of chronic pancreatitis and reflux esophagitis (ONO Pharmaceutical, 2009). It has been shown in vivo to inhibit TMPRSS2 thereby blocking viral entry into host cells (Hoffmann et al., 2020a). In similar disease of SARS, caused by SARS-CoV, which uses similar mechanism of entry, camostat treatment also improved survival times in a mouse model of SARS-CoV infection (Zhou et al., 2015). We hypothesize that inhibition of TMPRSS2 with camostat, by treating early in the disease course when patients are diagnosed as outpatients, will decrease the percentage of people who end up hospitalized from COVID-19.

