### 3.1. Inclusion Criteria

1.  $\geq 60$  years of age
2. COVID-19 infection, confirmed by polymerase chain reaction (PCR) test  $\leq 5$  days from enrollment done in the ambulatory setting
3. Able to provide informed consent
4. Symptom related to COVID-19. This includes: fever or chills, cough, shortness of breath or difficulty breathing, fatigue, muscle or body aches, headache, new loss of taste or smell, sore throat, congestion or runny nose, nausea or vomiting, diarrhea or other symptom recognized by the Centers for Disease Control to be a symptom of COVID-19.

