### 3.2. Exclusion Criteria

1. Patients who undergo asymptomatic screening test that is positive and remain asymptomatic during the eligible time window
2. Patients who have had one or more positive tests more than 5 days prior to enrollment but within 60 days of enrollment (ex. If a patient has a positive test 10 days prior to enrollment and then a second positive test the day referred for enrollment, that patient would be excluded. If a patient had a positive test 5 months ago, and then another positive test the day he/she was referred for enrollment, that patient would be eligible.)
3. Unable to take oral medication

4. Male patients with female partners of reproductive potential who are unable to maintain effective contraception during the recommended time period (during treatment and for 130 days after the final dose)
5. Symptoms requiring hospitalization or immediate referral to hospital
6. Taking bicalutamide, any systemic hormonal therapy, or camostat within one month of study entry
7. Known hypersensitivity to bicalutamide, or camostat, or its components.
8. On coumadin anticoagulation (because of drug-drug interaction with bicalutamide)
9. Self-reported past medical history of chronic liver disease or cirrhosis
10. Self-reported myocardial infarction within 6 months or past medical history of congestive heart failure with known ejection fraction < 40%
11. Taking any other investigational treatment for COVID-19 or COVID-19 prophylaxis (COVID-19 vaccines and treatments allowed under FDA Emergency Use Authorization are allowed.)

[figure not shown]

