## 4. Treatment Plan

### 4.1. Study design

This will be a randomized, open-label study to determine if camostat+ bicalutamide decreases the proportion of people with COVID-19 who require hospitalization, compared to historical controls. Patients with symptomatic COVID-19, diagnosed as outpatients, will be randomized 1:1 stratified by gender and receipt of SOC drugs/vaccine, to treatment with standard of care alone or with camostat+bicalutamide . The schema is shown below:

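### Illness duration at entry is recorded to an end point not defined for the control arm, and the planned symptom comparison does not use it

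*Combined protocol and SAP*

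**What the plan says.** Timing at entry is set by test dates. Section 3.1 requires infection "confirmed by polymerase chain reaction (PCR) test" no more than 5 "days from enrollment done in the ambulatory setting", and section 3.2 excludes "Patients who have had one or more positive tests more than 5 days prior to enrollment but within 60 days of enrollment". Section 3.1 also asks for a "Symptom related to COVID-19", with no maximum time since onset. Sections 6.2 and 6.3 stratify by gender and by receipt of standard-of-care drugs or vaccine, not by duration of illness.

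One item measures that duration, a footnote to the baseline symptom row of the study calendar (section 10): "Record the number of days between the onset of symptoms and initiation of treatment". The row is not limited to one arm.

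Section 11.2 gives the symptom analysis in one sentence: "The proportion of people with symptoms will be compared to the proportion of people without symptoms and compared using chi-squared test". It names no covariate. I read it as an arm-to-arm comparison, because sections 2.2 and 2.5 require one. Its literal wording is a separate fault.

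Section 1.1 puts the camostat hypothesis in terms of benefit "by treating early in the disease course when patients are diagnosed as outpatients".

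**The concern.** Whether a patient still has symptoms on day 7 or day 21 plausibly depends on how long that patient had already been ill at entry. Two patients tested on the same day may be at quite different stages. With 40 patients, randomization can leave one arm further along by chance, and the unadjusted difference then mixes drug effect with illness stage.

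The trial intends to collect the variable that would deal with this, but its end point is loose and no analysis uses it. At stake are the precision and readability of a secondary endpoint in a trial about early treatment. Section 11 says the trial's estimates will feed the sample size of a confirmatory study.

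**Working it through.** **The plan's own figures.** There is no power figure for symptoms. The only one is for hospitalization (section 11): 80% for 20% v 2%, 20 per arm, one-sided Fisher test at 0.25. Exact enumeration gives 80.3%, so it reproduces. It does not bear on this point.

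**What the footnote measures in each arm.**
- Experimental arm: duration = (onset to randomization) + (randomization to first dose). Section 6.2 allows the second term to reach 72 hours, and section 4.6 allows drug to be shipped.
- Control arm: section 4.1 randomizes patients "to treatment with standard of care alone or with camostat+bicalutamide", and the calendar marks standard of care for both arms on days 1 to 7. The word treatment therefore covers this arm, but no event is named as its start.

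Suppose the control value were taken to randomization and the experimental value to first dose. A gap of up to 3 days could then arise from definition alone. At the slopes assumed below, that would move an adjusted comparison by up to 3 × 0.2 = 0.6 to 3 × 0.4 = 1.2 log-odds. This is an upper bound, but it shows that the field as worded should not be used as a covariate.

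**Chance imbalance.** Inputs: 20 per arm (40 patients, 1:1; sections 3 and 6.2). The SD of onset-to-entry time is an assumption.
- SE of the difference in means = SD × √(2/20).
- At SD 3: SE = 3 × 0.316 = 0.95 days, and P(|difference| > 1 day) = 2 × [1 − Φ(1/0.95)] = 29%.

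| Assumed SD (days) | SE (days) | P(difference > 1 day) |
|---|---|---|
| 2 | 0.63 | 11% |
| 3 | 0.95 | 29% |
| 4 | 1.26 | 43% |
| 5 | 1.58 | 53% |

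**Validity of the unadjusted test.** Simulated with no drug effect and assumed symptom rates of 70/50%, 80/40% or 90/30% for short/long duration, the chi-squared test at two-sided 0.05 rejects in 4.7% to 4.9% of trials.

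**Day-7 power with and without adjustment.** Assumptions: control log-odds of symptoms 0.4 at mean duration, treatment effect −1.2, onset SD 3 days, linear models, two-sided 0.05, 3,000 trials per slope. The implied reduction is about 23 to 27 percentage points.

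| Fall in log-odds per day ill | Unadjusted | Adjusted | Gain (points) |
|---|---|---|---|
| 0.2 | 38.9% | 42.6% | 3.7 |
| 0.3 | 35.1% | 41.4% | 6.3 |
| 0.4 | 28.5% | 36.4% | 7.9 |

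Runs of 6,000 trials agree to within about 2 points. At slope 0.1 they give 41% v 43%. At slope 0 the adjusted model still shows 43.9% v 42.6%, so roughly 1 point of each gain is not due to adjustment. The empirical SE of the risk difference falls from 0.151 to 0.148 at slope 0.2, and from 0.153 to 0.144 at slope 0.3.

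**Day 21.** With an assumed 25% of controls symptomatic, unadjusted v adjusted power is 27.2% v 27.0% (slope 0.2) and 24.7% v 26.1% (slope 0.3).

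**Size of the distortion when imbalance occurs.** With no drug effect and the drug arm more than 1 day further into illness, the unadjusted difference averages about 6 to 11 points in the drug's favor at slopes 0.2 to 0.4. The adjusted one averages within about 1 point of zero.

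**The case against.** The best defense is that nothing here is invalid. Randomization balances illness duration in expectation, type I error holds, and the confidence interval already allows for chance imbalance. An unadjusted comparison is a legitimate choice in a 40-patient study, and age and comorbidity are not adjusted for either. The gain rests wholly on assumed inputs, is close to nothing at day 21, and leaves day-7 power below about 45%. A covariate model with few symptomatic patients brings model dependence. Entry stage is also partly constrained by the 5-day test window. All of this stands, and it keeps the point minor.

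Three stronger readings are tempting, and the documents support none of them.
- A reader might infer that control patients have no treatment start, so the footnote has no value for them. Sections 4.1, 6.2 and 10 all apply treatment to both arms. The start is undefined, not absent.
- A reader might infer that adjustment is impossible. Completing the footnote requires knowing when symptoms began, and every patient has a randomization date. Onset to randomization can be derived if the onset date is kept. The footnote, however, asks for a number of days, not the date.
- A reader might infer that the symptom comparison is biased. Under randomization the cost is precision and interpretation, not systematic error.

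The defense does not remove the loose end point. Reading standard of care as treatment still leaves each site to choose its start, while the experimental arm may carry up to 3 days of delay after randomization.

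**Conclusion.** The point holds as a minor one. Entry and stratification leave illness duration free, the single measure of it may not be comparable between arms, and section 11.2 makes no use of it.

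Under an assumed onset SD of 3 days, the price is a 29% chance of a mean difference above 1 day and about 4 to 8 points of day-7 power at slopes of 0.2 to 0.4. There is little to gain at slope 0.1 or at day 21. The SD, slopes, symptom rates and treatment effect are all assumptions, because the documents supply none. The validity of the symptom test and the primary endpoint are not in question.

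**What to change.** 1. In the section 10 footnote, record the symptom onset date and the number of days from onset to randomization for every patient in both arms. Randomization is a date common to both arms, and section 11.1 already counts the primary endpoint from it.
2. In section 11.2, pre-specify the between-arm comparison of symptoms at day 7 adjusted for days since onset, reported as a standardized risk difference with the unadjusted difference beside it.
3. Do the same at day 21 as a supportive analysis, if there are enough symptomatic patients to fit the model.
4. Leave eligibility unchanged.

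The cost is one reworded footnote and one or two analysis sentences, and the footnote already requires onset to be established at baseline. The downside is one covariate with 40 patients and some model dependence, which reporting the unadjusted result keeps visible. Fixing the covariate in advance also avoids a later choice of adjustment in an open-label trial.
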